[name] and his colleagues conducted a randomized phase II trial from October 2011 to January 2012, in which 267 healthy volunteers in Qidong City, China (a region with extremely high liver cancer prevalence) received 84 consecutive daily doses of a broccoli sprout beverage containing 600 μ mol of glucoraphanin and 40 μ mol of sulforaphane, or an indistinguishable placebo (17). The study participants comprised 136 treated with broccoli sprout beverage and 131 placebo controls. Of the 267 participants completing the study, 50% consumed all assigned doses, and the remaining participants consumed at least 80 of the 84 doses. Extensive blood chemistries at the termination of the study showed that the means of 13 analytes were identical between treated and control groups, and that specifically no abnormalities were detected in BUN, creatinine, and transaminases (ALT and AST). Three individuals, 2 in the placebo arm and 1 in the treated arm, had slightly elevated total bilirubin (1.1, 1.6, 1.8 mg/dL) and two individuals, 1 each in placebo and treated arms, had slightly elevated direct bilirubin (0.5, 0.6 mg/dL levels).

4.1.7 Rationale for Selected Doses

We will use doses of Avmacol® that will provide equivalent concentrations of SF as found in our most recent trials of various BSP preparations. Four Avmacol® tablets twice daily will provide an internal dose of 120 micromole SF per day. The dose selection is based on the results of our previous clinical trials (NCT02023931) with the maximum tolerable dose and minimal toxicity effect to maximize the biological effect (17,59).

This dose level represents bioactive and tolerable doses in healthy volunteer studies. This dose was found to be tolerable and without safety compromise with no grade 2 or higher toxicities reported. Although bad taste was the main complaint by study subjects consuming beverage made from SF-rich sprouted broccoli seed powder at 150 μ mol/day, the encapsulation of Avmacol® is expected to mask any issues with

taste. This dose is expected to achieve a target level of NRF2 pathway activation based on a previous healthy volunteer study (59). The twice-daily dosing schedule will provide a steady level of in vivo SF over the 24 hr a day, as shown in a recent report (60).

4.2 Rational for Proposed Study in High-Risk Former Smokers

It is critical to carefully define entry criteria for any lung cancer prevention trial. Study subjects must be of high enough risk that either lung cancer or intermediate endpoints will be found as frequently as possible. We have created a unique high-risk cohort of approximately 3,600 current and former smokers, the Pittsburgh Lung Screening Study (PluSS). At baseline, we administered a risk factor questionnaire, tested pulmonary function, assessed low-dose computed tomography (LDCT) for emphysema severity, created a biorepository (serum, plasma, and DNA), and implemented procedures to ascertain and characterize new lung cancer diagnoses. At enrollment, PluSS participants had a mean age of 60 years. Among the participants, 49% were women; 93% whites, 5.5% blacks, and 1.7% other race/ethnicity groups; 60% current smokers and 40% former smokers with a median 47 pack-years of smoking history (61). The PluSS participants resembled the national representative sample of current and former smokers who are at high risk for lung cancer. For example, the National Lung Screening Trial (NLST) enrolled more than 53,000 persons at high risk for lung cancer at 33 medical centers across the US. The mean age was 61 years. Forty-one % were women; 91% whites, 4% blacks, and 5% other race/ethnicity groups; 48% current smokers and 52% former smokers who quit smoking within the previous 15 years; a median 48 pack-years of smoking history (62).

This unique cohort has contributed many scientific discoveries in risk biomarkers of lung cancer (61,63-72). For example, the presence of chronic obstructive pulmonary disease (COPD) significantly increased lung cancer risk (61,66). Compared with smokers without COPD, smokers with COPD measured as the Global Initiative for Chronic Obstructive Lung Disease (GOLD) II or higher or Forced Expiratory Volume in the first second (FEV1) < 80 % had more than doubled risk of developing lung cancer after controlling for smoking intensity and duration (**Table 2**).

Table 2. Hazard ratios (HRs) of lung cancer associated with baseline airflow obstruction and radiographic emphysema in the Pittsburgh Lung Screening Study

	Cases	Noncases	Adj. HR (95% CI)*
Airflow obstruction			
None	32	2053	1.00
GOLD I	16	477	1.66 (0.89-3.11)
GOLD II	36	792	2.11 (1.27-3.49)
GOLD III-IV	15	217	2.86 (1.48-5.53)
P for trend			0.005
Radiographic emphysema			
None	24	2068	1.00
Trace	22	663	2.58 (1.43-4.66)
Mild	37	493	5.04 (2.94-8.62)
Moderate/severe	16	315	3.20 (1.65-6.23)
P for trend			<0.0001

* Adjusted for age, sex, years of cigarette smoking, and number of cigarettes per day.

The presence of mild, moderate or severe radiographic emphysema on the LDCT scans at baseline was significantly associated with a 3- to 5-fold increased risk of developing lung cancer compared to smokers without emphysema (61).

We will recruit subjects for the present study from the existing PluSS participants who had mild, moderate or severe emphysema or GOLD II-IV COPD. Among the original PluSS participants who, as of 12/31/2015, were <75 years old, alive, free of cancer, and had quit smoking within the past 15 years, 356 had GOLD II-IV COPD (with or without emphysema), and additional 167 with mild, moderate or severe emphysema (without COPD). All these 523 subjects are potentially eligible for the proposed study. Based on our previous experience in the Iloprost study (22), which used a very similar protocol as the one proposed here, there was a 20% recruitment rate. Thus, we expect to fulfill our recruitment goal of at least 72 former smokers into the study within the first 3 years of the proposed study. With a 20% dropout rate based on our previous experience (22), we expect to have 60 study subjects who will complete the entire course of the trial.

If the proposed chemopreventive agent is effective, it will bring beneficial effect for study participants on reducing their risk of lung cancer. After the end of the study, all study participants can conduct their oral intake of Avmacol® since this dietary supplement is relatively cheap and commercially available.

5. TREATMENT PLAN AND STUDY PROCEDURES

5.1 Pre-Treatment Evaluation

Pretreatment tests should be performed within 90 days prior to the randomization.

- 1) Signed informed consent
- 2) Questionnaire data collection on patient's characteristics and smoking history.
- 3) Physical exam including height, weight, vitals and SWOG performance status.
- 4) FEV1/FVC
- 5) Blood oxygen saturation
- 6) Expired Carbon Monoxide
- 7) Laboratory analysis including CBC and serum chemistries such as total bilirubin, AST, ALT, BUN, creatinine, .
- 8) Baseline bronchoscopy: Prior to randomization, all participants will undergo a bronchoscopy at the Endoscopy Suite at the UPMC Shadyside Hospital. The procedure will be carried out by [name] (Co-PI) using Narrow Band Imaging (NBI) white-light bronchoscopy. The patient's nose, throat, vocal cords and windpipe are sprayed with Lidocaine (numbing medicine) to help keep patient from coughing and to numb patient's airways. During the procedure, [name] will perform a complete airway examination including visualization of the vocal cords, trachea, main carina, and orifices of the sub-segmental bronchi to the extent that it is visible without causing trauma to the bronchial wall. Biopsy samples will be collected at the pre-determined sites. Some of these biopsies will be used for the pathological examination. Any patients with lung cancer or carcinoma in situ will be ineligible for the present study. We will inform subjects the abnormal biopsy results and provide appropriate counseling from qualified medical personnel.

Since the clinical significance of moderate or severe dysplasia is unknown and no effective treatment available, we will not conduct additional clinical procedure or intervention on these patients beyond routine follow-up and care. The patients with dysplasia will be monitored at each clinical visit (once every three months during the treatment period) according to the study protocol. At the end of study period, another biopsy at the same site of initial locations that show dysplasia will be performed to evaluate the change (progress, regress or no change) of these lesions detected at baseline biopsy. This is one of the primary outcome measures for the proposed study. After the completion of the study, the patients will continue to receive routine medical care including annual CT screening if eligible.

5.2 Randomization

Eligible subjects will be randomly assigned to either Avmacol® or placebo arm with a 50%-50% chance. Each subject will be given three bottles of tablets at month 0 and at trimonthly clinical visits. Each bottle contains 250 tablets that will be sufficient for one month supply.

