5.3.2 Dose

Following randomization, subjects will begin to take four study tablets (Avmacol or placebo) in the morning with breakfast and four tablets in the evening with dinner. Each tablet contains 15 mg of glucoraphanin (GR), but contains no SF. Thus the daily ingested dose is 120 mg or 274.29 micromole GR (molar mass 437.49). Based on our most recently completed bioavailability studies in humans (48), the internal conversion rate of GR to SF in standard gelcaps (the same formula for the present study) was 44% (see Table 1 – Cohort 5 under Section 5.5.1 Pharmacokinetics and Metabolism in Humans on page 23). Thus the 8 Avmacol tablets provide a daily internal dose of approxi 120 micromole SF ($274.29 \times 0.44 = 120.68$ micromole SF).

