5.3.3 Treatment Duration

The Avmacol tablets will be administered to study participants for a total duration of 12 months. Data regarding the duration of SF administration on altering cellular

markers in human bronchial tissues are lacking. In a recent phase 2 clinical trial lasting 2-8 weeks, Atwell *et al.* evaluated the effect of SF on level of Ki-67 LI in breast benign tissue in women who underwent diagnostic biopsy and surgical treatment for breast cancer. The daily dose of 513 micromole glucoraphanin (SF precursor) significantly reduced Ki-67 expression in the benign breast tissue ($P<0.01$) (16). We note the conversion rate for this formulation of glucoraphanin to SF was not determined by the authors (16). It is likely lower than our Avmacol formulation: typically 5% in the absence of myrosinase. Our Avmacol tablets provide optimal internal dose of SF on apoptosis/proliferation markers, by pushing the duration of SF administration to 12 months.

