5.5 Clinical Visits

Besides two clinical visits in stage 1 of the study for eligibility screening, all eligibility study participants will begin taking the study tablets at visit 1 of stage 2 of the study and return to the study clinic at the end of months 3, 6, 9, and 12 (the end of treatment period). At each clinical visit, the clinical research nurse/assistant will conduct the following:

- 1) Exam the subject's diary for dosing and timing of intake of test tablets, and keep the diary in subject's folder.
- 2) Count and record the remaining tablets given.
- 3) Provide new study tablets that will supply the next 3 months.
- 4) Study participant will turn in the self-administered questionnaire for recording his/her intake of cruciferous vegetables in the past 3 months using a dietary frequency questionnaire (Appendix 5).
- 5) Collect blood, spot urine and nasal brushing samples
- 6) Conduct pulmonary function test: FEV1/FVC
- 7) Collect safety and toxicity measures at each clinical visit (once every 3 months) during the 12-month treatment period:
 - a) Collect adverse events (AEs) using the AE Recording Form (Appendix 8)

- b) Conduct physical examination including body weigh, height, and vitals by a registered nurse and record the results in the patient's study file
- c) Laboratory evaluation: CBC with platelets and differential, chemistry panel including liver function testing.
- 8) Only at the end of treatment period, bronchoscopy will be performed on the patient using the same procedure as described above in 5.1(8) and bronchial biopsies and lavage samples collected (stage 2- visit 5).

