6. STUDY CALENDAR

		Stage 1		Stage 2 (after randomization)						Post-treatment		
		Pre-clinical	#1	#1	#2	#2	#3	#4	#5	#6	Phone	Mail
Clinical visit	Targeted Date			Day 0*	Day 90±14	Day 180±14	Day 270±14	Day 360±14	Day 367±10		1 mo. after	1 yr. after
Eligibility Screening Form	Phone Interview											
MAIL OUT FORMS												
Locator Form	(mail)	(Rec)										
Baseline Questionnaire	(mail)	(Rec)						(mail)		(Rec)		
Cruciferous Vegetable intake form (compliance)					X	X	X	X		X		
SIGN CONSENT FORM	(PluSS PID)	X										
Assign subject ID (SF-Seq #)†		SF-001 SF-002 ...										
PHYSICAL EXAM												
Vitals, weight & height		X			X	X	X	X		X		
CO test		X			X	X	X	X		X		
O2 test		X										
Spirometry (PFT)		X			X	X	X	X		X		
Urinary Pregnancy Test		X										
BLOOD (for Screening or AE Monitoring)												
CBC/platelets		X				X	X	X		X		
Chemistry panel & LFT		X				X	X	X		X		
BRONCHOSCOPY												
Bronchial biopsy			X							X		
Bronchial brushing			X							X		
Bronchoalveolar lavage			X							X		
INCLUSION/EXCLUSION FORM	(X)	(X)	(X)									
TREATMENT ASSIGNMENT (TA-Seq #)‡				TA-001 TA-002 ...								
Provide study tablets (for 3 months)				X	X	X	X					
Pill count in returned bottles					X	X	X			X		
RESEARCH SAMPLES												
Blood					X	X	X	X		X		
Nasal brushing					X	X	X	X		X		
Spot urine					X	X	X	X		X		
AE ASSESSMENT FORM					X	X	X	X		X		
COMPENSATION		\$50	\$500	\$50	\$50	\$50	\$50	\$500	\$500			
Provide parking ticket		X	X	X	X	X	X	X	X			
FOLLOW-UP											X	X
General health											X	X
Lung cancer											X	X
Any cancer											X	X

* Day 0 is when the subject is given a treatment assignment number.

† Study subject ID is assigned right after the consent form is signed by a potential eligible subject. This number will be used for the entire study and all forms and sample collection sheets.

‡ Treatment assignment number is TA-sequential # of subjects entering into stage 2 of the study. the TA # randomly determines the subject's treatment arm..

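### One dispensing of three bottles lasts 93.75 days, which does not reach the end of the ±14-day visit window, and the plan does not say whether unused tablets carry forward

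*Combined protocol and SAP*

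**What the plan says.** **Supply.** Section 5.2: "Each subject will be given three bottles of tablets at month 0 and at trimonthly clinical visits". On bottle size it adds: "Each bottle contains 250 tablets that will be sufficient for one month supply". Section 5.5 describes the resupply at each visit as: "Provide new study tablets that will supply the next 3 months". No extra quantity for a late visit is mentioned.

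**Consumption.** Section 5.3.2 has participants take "four study tablets (Avmacol or placebo) in the morning with breakfast and four tablets in the evening with dinner", which is 8 a day. Section 5.3.3 says the tablets are "administered to study participants for a total duration of 12 months".

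**Visit timing.** The Section 6 calendar sets visits at Days 90, 180, 270 and 360, each ±14 days, and a further visit at Day 367±10. Section 5.5 places the second bronchoscopy at stage 2 visit 5, the Day 360 visit, so it may fall as late as Day 374.

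**Leftovers.** Section 5.5 has remaining tablets counted and recorded. The calendar row reads "Pill count in returned bottles". Section 11.5 requires the returned quantity to be logged and also asks for empty containers to be returned. I found no statement on whether unused tablets are collected, kept or re-issued.

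**The concern.** Each dispensing is sized for three calendar months with a few days to spare, while the calendar allows a visit two weeks late. A participant who takes every tablet and attends within the window can therefore run out, through supply rather than behaviour.

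The most sensitive place for such a gap would be just before visit 5. The post-treatment tissue for the dysplasia index, Ki-67, caspase-3, TUNEL and bronchial gene expression is taken there (Sections 9.1 to 9.3). Section 4.1.5.1 gives a plasma half-life of 1.77 hours for the isothiocyanate metabolites and says most induced phase 2 enzymes have half-lives measured in days. Against those times, one to three weeks off tablets is long. If it happened in the sulforaphane arm, it could dilute the faster-moving readouts.

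**Working it through.** **Inputs.** 250 tablets per bottle and 3 bottles per dispensing (5.2); 8 tablets a day (5.3.2); dispensing at Day 0 and at the Day 90, 180 and 270 visits (5.2, 6); windows of ±14 days (6); bronchoscopy at visit 5 (5.5). Full adherence is assumed; missed doses would stretch the supply.

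**The plan's own figure.** 250 / 8 = 31.25 days per bottle, so one month per bottle is right. Per dispensing, 3 × 250 = 750 tablets and 750 / 8 = 93.75 days. A 90-day interval needs 90 × 8 = 720 tablets, leaving 30 spare.

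**First interval, which needs no assumption about leftovers.** The latest permitted visit is 90 + 14 = Day 104. Need: 104 × 8 = 832. Shortfall: 832 − 750 = 82 tablets, or 82 / 8 = 10.25 days. No earlier dispensing exists to draw on, and later bottles have not yet been handed out.

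**Before the bronchoscopy, if unused tablets are collected at each visit.** Days off tablets = bronchoscopy day − (last dispensing day + 93.75), or zero if negative.

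| Last dispensing | Tablets end | Bronchoscopy Day 360 | Bronchoscopy Day 374 |
|---|---|---|---|
| Day 256 | 349.75 | 10.25 | 24.25 |
| Day 270 | 363.75 | 0 | 10.25 |
| Day 284 | 377.75 | 0 | 0 |

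The longest permitted last interval is 374 − 256 = 118 days. It needs 118 × 8 = 944 tablets, 194 more than supplied, and 194 / 8 = 24.25 days.

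**Before the bronchoscopy, if unused tablets are kept.** Four dispensings give 4 × 750 = 3,000 tablets, and 3,000 / 8 = 375 days. Need to Day 374: 374 × 8 = 2,992, leaving 8 spare, which is one day. A day-by-day check with each dispensing visit at the early edge, target or late edge of its window found no gap before a bronchoscopy at Day 360 or Day 374.

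**Sensitivity.** If the procedure slipped to the last day of the visit 6 window (367 + 10 = Day 377), the need would be 377 × 8 = 3,016. That is 16 tablets, or 2 days, short even with leftovers kept.

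**The case against.** The strongest reply is that no stated figure is wrong. The one-month sentence is accurate, and three bottles cover three months with 3.75 days to spare. That stands: this is a mismatch between two sections for late visits, not an arithmetical error in either.

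A reader might infer that participants will be off tablets before the month-12 biopsies. The documents do not support that. It requires leftovers to be collected. The returned-bottle count and the log of returned quantities point that way, but returned bottles may simply be brought in for counting, and the request for empty containers fits participants who finish their supply. If leftovers are kept, the total supply reaches past Day 374.

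Even with collection, most of the gap after a Day 270 dispensing lies beyond a 365-day year: 374 − 365 = 9 of the 10.25 days. The 24-day figure needs opposite window edges at consecutive visits. Both points are fair. However, a Day 256 dispensing followed by an on-target Day 360 bronchoscopy also gives 10.25 days, all within 12 months.

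A reader might also infer that the primary endpoint is pulled toward the null. Nothing in the documents shows that the dysplasia index would revert within days, and Section 4.1.5.1 itself says a high cellular concentration need not be continuous. Nor do they show that a supply gap would lower measured adherence: no adherence measure is defined, and the pill count of someone who ran out shows every dispensed tablet gone.

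**Conclusion.** The point holds as a minor one. The quantity dispensed does not cover the plan's own permitted interval. At full adherence, the first interval can leave a participant without tablets for up to 10.25 days under any rule on leftovers.

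A gap before the visit 5 bronchoscopy is conditional on unused tablets being collected, which is suggested but not stated. On that condition it is up to 10.25 days after a Day 270 dispensing and up to 24.25 days in the extreme case. Without it, there is no gap up to Day 374, with one day to spare.

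Dilution is more plausible for Ki-67, apoptosis and gene expression than for the dysplasia index. Its size cannot be derived, because the documents give neither the frequency of late visits nor the rate at which these markers would revert.

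**What to change.** - Reconcile the dispensing quantity in Section 5.2 (and the resupply wording in 5.5) with the visit windows in Section 6, so that supply and permitted intervals agree at the protocol's own daily tablet count.
- State in Sections 5.5 and 11.5 whether unused tablets are kept by the participant or collected at each visit.
- Capture the date of the last tablet before the second bronchoscopy. The intake diary in the recording part of Section 5.3.4 already holds the information, so this needs one data field.

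The cost is some additional tablets and minor edits to the dispensing instructions. Sample size and analysis are unaffected. No dose or visit schedule is proposed here; how the sections are brought into agreement is for the investigators to decide.

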5.3 Treatment Plan

5.3.1 Nutraceutical Information

Please see the Avmacol® Nutraceutical Information Guide for detailed information on manufacturing and quality assurance (Appendix 11).

For this study, capsules will be shipped from Nutramax to the University of Pittsburgh as follows:

c/o [name]
Director, Investigational Drug Service
UPMC Hillman Cancer Center
Ground Floor, AG40.3
[name]
Pittsburgh, PA 15232

Avmacol® capsules will be stored at room temperature in the Investigational Drug Pharmacy at the UPMC Hillman Cancer Center. After dispensing, they may be stored at room temperature at the participant's home.

5.3.2 Dose

Following randomization, subjects will begin to take four study tablets (Avmacol or placebo) in the morning with breakfast and four tablets in the evening with dinner. Each tablet contains 15 mg of glucoraphanin (GR), but contains no SF. Thus the daily ingested dose is 120 mg or 274.29 micromole GR (molar mass 437.49). Based on our most recently completed bioavailability studies in humans (48), the internal conversion rate of GR to SF in standard gelcaps (the same formula for the present study) was 44% (see Table 1 – Cohort 5 under Section 5.5.1 Pharmacokinetics and Metabolism in Humans on page 23). Thus the 8 Avmacol tablets provide a daily internal dose of approxi 120 micromole SF ($274.29 \times 0.44 = 120.68$ micromole SF).

5.3.3 Treatment Duration

The Avmacol tablets will be administered to study participants for a total duration of 12 months. Data regarding the duration of SF administration on altering cellular

markers in human bronchial tissues are lacking. In a recent phase 2 clinical trial lasting 2-8 weeks, Atwell *et al.* evaluated the effect of SF on level of Ki-67 LI in breast benign tissue in women who underwent diagnostic biopsy and surgical treatment for breast cancer. The daily dose of 513 micromole glucoraphanin (SF precursor) significantly reduced Ki-67 expression in the benign breast tissue ($P<0.01$) (16). We note the conversion rate for this formulation of glucoraphanin to SF was not determined by the authors (16). It is likely lower than our Avmacol formulation: typically 5% in the absence of myrosinase. Our Avmacol tablets provide optimal internal dose of SF on apoptosis/proliferation markers, by pushing the duration of SF administration to 12 months.

